**Table 2-3: Open-Label Phase Procedural Outline**

| Procedure                              | Wk 1 a | Wk 2
±1 day | Wk 3
±1 day | Wk 6
±3 days | Wk 12
±3days | Wk 18
±3days | Wk 24
±3days | Wk 36
±3days | Wk 48/
or early
D/C
±3 days | Wk 60
±5 days | Wk 72 to
Wk 192
±5 days | Notes
Week 1 of the open-label phase occurs 1 week
after the end of the Week 48 double-blind visit
After Week 24 visits to take place every
12 weeks   |
|--|-------------------|----------------|----------------|-----------------|-----------------|-----------------|-----------------|-----------------|--------------------------------------|------------------|-------------------------------|--|
| Safety Assessments              |                   |                |                |                 |                 |                 |                 |                 |                                      |                  |                               |  |
| Electrocardiogram (ECGs)               |                   |                |                |                 |                 |                 |                 |                 | X                                    |                  | X                             | ECGs should be recorded after the participant has been supine for at least 5 minutes. See Eli 150c/250c User Guide; to be assessed every 24 weeks after Wk 48 of OL phase.   |
| Laboratory Tests                       | X                 |                |                |                 | X               |                 | X               | X               | X                                    | X                | X                             | Placement of an intravenous lock is allowed for onsite visits when multiple blood draws are required.  |
| Urinalysis                             |                   |                |                |                 | X               |                 | X               | X               | X                                    | X                | X                             |  |
| Monitor for Non-Serious Adverse Events | X                 | X              | X              | X               | X               | X               | X               | X               | X                                    | X                | X                             | See notes above.
Falls should be assessed at each study visit b .  |
| Monitor for Serious Adverse Events     | X                 | X              | X              | X               | X               | X               | X               | X               | X                                    | X                | X                             | See notes above.
All SAEs must be collected from the date of participant’s written consent until 50 days post discontinuation of dosing in the present study. If the participant enters a separate rollover treatment study of RO7239361, the participant’s SAEs will be reported in that study.
Falls should be assessed at each study visit b . |
| Blood PK Sampling                      | X                 | X              | X              |                 | X               |                 | X               | X               | X                                    |                  |                               | Must be collected prior to administration of study drug. See section 9.4 for the sample collection schedule.   |
| TFTs                                   | X                 |                |                |                 |                 |                 | X               |                 | X                                    |                  | X                             | See Clinical Evaluator Manual Functional measures at Open Label Week 1 Visit must be obtained prior to dosing; TFT assessment must be videotaped for ATOM review at Wk 24 and Wk 48 visits. To be assessed every 24 weeks after Wk 48 of the OL phase.   |

**Table 2-3: Open-Label Phase Procedural Outline**

| Procedure                 | Wk 1 a | Wk 2
±1 day | Wk 3
±1 day | Wk 6
±3 days | Wk 12
±3days            | Wk 18
±3days | Wk 24
±3days             | Wk 36
±3days             | Wk 48/
or early
D/C
±3 days | Wk 60
±5 days | Wk 72 to
Wk 192
±5 days | Notes
Week 1 of the open-label phase occurs 1 week
after the end of the Week 48 double-blind visit
After Week 24 visits to take place every
12 weeks  |
|---------------------------|-------------------|----------------|----------------|-----------------|----------------------------|-----------------|-----------------------------|-----------------------------|--------------------------------------|------------------|-------------------------------|---|
| Safety Assessments |                   |                |                |                 |                            |                 |                             |                             |                                      |                  |                               |   |
| 6MWD                      | X                 |                |                |                 |                            |                 | X                           |                             | X                                    |                  | X                             | See Clinical Evaluator Manual
Functional measures at OL Week 1 visit must be
obtained prior to dosing; 6MWD assessment must
be videotaped for ATOM review at Wk 24 and
Wk 48 visits. To be assessed every 24 weeks after
Wk 48 of the OL phase.        |
| NSAA                      | X                 |                |                |                 |                            |                 | X                           |                             | X                                    |                  | X                             | See Clinical Evaluator Manual Functional
measures at OL Week 1 visit must be obtained
prior to dosing; NSAA assessment must be
videotaped for ATOM review at Wk 24 and Wk
48 visits. To be assessed every 24 weeks after Wk
48 of the OL phase.        |
| ActiMyo                   |                   |                |                |                 | X
(Wk 6
to
Wk 12) |                 | X
(Wk 18
to
Wk 24) | X
(Wk 30
to Wk
36) | X
(Wk 42
to
Wk 48)          |                  |                               | Subjects at selected sites who opt in during the
double-blind phase of the study will wear the
ActiMyo device at home and during visits of the
OL phase. See the ActiMyo manual.   |
| PUL                       | X                 |                |                |                 |                            |                 | X                           |                             | X                                    |                  | X                             | See Clinical Evaluator Manual Functional
measures at Open Label Week 1 Visit must be
obtained prior to dosing; PUL assessment must be
videotaped for ATOM review at Wk 24 and Wk
48 visits. To be assessed every 24 weeks after Wk
48 of the OL phase. |
| PODCI                     |                   |                |                |                 |                            |                 | X                           |                             | X                                    |                  |                               | Completed by parent/caregiver (should be the
same parent/caregiver at each visit)  |
| CGI-C                     |                   |                |                |                 |                            |                 |                             |                             | X                                    |                  |                               | Completed by clinician (e.g., Principal
Investigator or other clinician who has
interacted with the individual from baseline)
Should be the same clinician at both visits.  |

**Table 2-3: Open-Label Phase Procedural Outline**

| Procedure                                       | Wk 1 a | Wk 2
±1 day | Wk 3
±1 day | Wk 6
±3 days | Wk 12
±3days | Wk 18
±3days | Wk 24
±3days | Wk 36
±3days | Wk 48/
or early
D/C
±3 days | Wk 60
±5 days | Wk 72 to
Wk 192
±5 days | Notes
Week 1 of the open-label phase occurs 1 week
after the end of the Week 48 double-blind visit
After Week 24 visits to take place every
12 weeks   |
|---|-------------------|----------------|----------------|-----------------|-----------------|-----------------|-----------------|-----------------|--------------------------------------|------------------|-------------------------------|--|
| Safety Assessments                       |                   |                |                |                 |                 |                 |                 |                 |                                      |                  |                               |  |
| Immunogenicity Sampling                         | X                 | X              | X              |                 | X               |                 | X               |                 | X                                    |                  | X                             | Must be collected prior to administration of study drug. In the event of a positive immunogenicity response, additional NAB testing will be conducted. To be assessed every 24 weeks after Wk 48 of the OL phase.                                   |
| Serum Free Myostatin and Myostatin-Drug Complex | X                 | X              | X              |                 | X               |                 | X               | X               | X                                    |                  |                               | Must be collected prior to administration of study drug.   |
| Serum Biomarkers                                |                   |                |                |                 | X               |                 | X               | X               | X                                    |                  |                               |  |
| PFTs  | X                 |                |                |                 |                 |                 | X               |                 | X                                    |                  | X                             | To include FVC, % predicted FVC, FEV 1 , MEP, and MIP
See Clinical Evaluator Manual Functional measures at OL Week 1 visit must be obtained prior to dosing. To be assessed every 24 weeks after Wk 48 of the OL phase.               |
| Upper & Lower Extremity Myometry                | X                 |                |                |                 |                 |                 | X               |                 | X                                    |                  | X                             | See Clinical Evaluator Manual Functional measures at OL Week 1 visit must be obtained prior to dosing; myometry assessment must be videotaped for ATOM review at Wk 24 and Wk 48 visits. To be assessed every 24 weeks after Wk 48 of the OL phase. |
| Grip & Pinch Strength                           | X                 |                |                |                 |                 |                 | X               |                 | X                                    |                  |                               | See Clinical Evaluator Manual Functional measures at OL Week 1 visit must be obtained prior to dosing.   |
| Right Ankle Range of Motion                     | X                 |                |                |                 |                 |                 | X               |                 | X                                    |                  | X                             | See Clinical Evaluator Manual Functional measures at OL Week 1 visit must be obtained prior to dosing. To be assessed every 24 weeks after Wk 48 of the OL phase.   |

**Table 2-3: Open-Label Phase Procedural Outline**

| Procedure   | Wk 1 a | Wk 2
±1 day | Wk 3
±1 day | Wk 6
±3 days | Wk 12
±3days | Wk 18
±3days | Wk 24
±3days | Wk 36
±3days | Wk 48/
or early
D/C
±3 days | Wk 60
±5 days | Wk 72 to
Wk 192
±5 days | Notes
Week 1 of the open-label phase occurs 1 week
after the end of the Week 48 double-blind visit
After Week 24 visits to take place every
12 weeks   |
|---|-------------------|----------------|----------------|-----------------|-----------------|-----------------|-----------------|-----------------|--------------------------------------|------------------|-------------------------------|--|
| Safety Assessments   |                   |                |                |                 |                 |                 |                 |                 |                                      |                  |                               |  |
| Caregiver video assessment  |                   |                |                |                 |                 |                 | X               |                 | X                                    |                  |                               | Subjects at selected sites who opt in to participate in the caregiver video assessment during the double-blind phase will record videos at the specified timepoints. Visit window: + 2 weeks. See Section 9.1.6 and the Parent/Caregiver manual. |
| CaGI-C  |                   |                |                |                 |                 |                 |                 |                 | X                                    |                  |                               | Completed by parent/caregiver (who has been involved in the study from baseline) who opt in at selected sites. Should be the same parent/caregiver at each visit.  |
| HUI-3   |                   |                |                |                 |                 |                 | X               |                 | X                                    |                  |                               | Completed by parent/caregiver (should be the same parent/caregiver at each visit)  |
| Health Care Resource Utilization  | X                 |                |                |                 |                 |                 | X               |                 | X                                    |                  |                               | Protocol mandated procedures, tests, and encounters are to be excluded.  |
| PedsQL Family Impact Module   |                   |                |                |                 |                 |                 | X               |                 | X                                    |                  |                               | Completed by parent/caregiver (should be the same parent/caregiver at each visit)  |
| Pediatric Quality of Life Inventory Multidimensional Fatigue Scale (PedsQL MFS) |                   |                |                |                 |                 |                 | X               |                 | X                                    |                  |                               | Completed by parent/caregiver who opt in at selected sites (should be the same parent/caregiver at each visit).  |
| Cardiac MRI (At selected sites)   |                   |                |                |                 |                 |                 |                 |                 | X                                    |                  | X*                            | Visit window +/- 1 week.
Conducted at early termination if ≥ 24 weeks from previous cMRI.
See the imaging procedure manual. *To be assessed every 48 weeks during the OL phase.  |

**Table 2-3: Open-Label Phase Procedural Outline**

| Procedure                                       | Wk 1 a | Wk 2
±1 day | Wk 3
±1 day | Wk 6
±3 days  | Wk 12
±3days | Wk 18
±3days | Wk 24
±3days | Wk 36
±3days | Wk 48/
or early
D/C
±3 days | Wk 60
±5 days | Wk 72 to
Wk 192
± 5 days | Notes
Week 1 of the open-label phase occurs 1 week after the end of the Week 48 double-blind visit
After Week 24 visits to take place every 12 weeks  |  |
|---|-------------------|----------------|----------------|--|-----------------|-----------------|-----------------|-----------------|--------------------------------------|------------------|--------------------------------|---|--|
| Safety Assessments                              |                   |                |                |  |                 |                 |                 |                 |                                      |                  |                                |   |  |
| DXA   |                   |                |                |  |                 |                 | X               |                 | X                                    |                  | X                              | Visit window +/- 1 week.
Not required at early termination visit.
See Section 9.1.3.1 and the imaging procedure manual.
DXA is not required for subjects enrolled at sites in Germany. To be assessed every 24 weeks after Wk 48 of the OL phase.    |  |
| Randomize                                       | X                 |                |                |  |                 |                 |                 |                 |                                      |                  |                                | Participants originally randomized to active drug will continue to receive the dose to which they were originally randomized. Participants originally randomized to placebo will be randomized to the high or low dose of RO7239361 on Day 1 of the OL phase. |  |
| Weekly study drug administration                | X                 | X              | X              |  |                 |                 |                 |                 |                                      |                  |                                |   | RO7239361 will be administered every week (every 7 days, unless otherwise stated). The first 3 doses of RO7239361 (Week 1, Week 2 and Week 3) must be administered at the clinic.
Parents/caregivers can start administering at home starting at OL Week 4. Study drug, RO7239361, in pre-filled syringes for weekly study drug administration, will be dispensed as needed.
Parents/caregivers will be dispensed approximately 12-week supply of prefilled syringes RO7239361 for weekly study drug administration to the participant. On site study visit days, participants should be dosed in clinic, after PK, immunogenicity and myostatin sampling. |
| Access IWRS to obtain study drug kit assignment | X                 | X              | X              | X  | X               | X               | X               | X               | X                                    | X                | X                              | Supplied by Roche in pre-filled syringes  |  |

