**Table 2-2: On Treatment Procedural Outline, Double-Blind Phase**

| Procedure                                       | D1 a | D8
±1 day
(Wk 1) | D15
±1 day
(Wk 2) | D29
±1 day
(Wk 4) | Wk 6
±3 days | Wk 12
±3 days | Wk 18
±3 days | Wk 24
±3 days | Wk 30
±3 days | Wk 36
±3 days | Wk 42
±3 days | Wk 48 or
early D/C
±3 days | Notes   |
|---|-----------------|------------------------|-------------------------|-------------------------|-----------------|------------------|------------------|------------------|------------------|------------------|------------------|----------------------------------|---|
| Electrocardiogram (ECGs)                        | X               |                        |                         |                         |                 |                  |                  | X                |                  |                  |                  | X                                | ECGs should be recorded after the participant has been supine for at least 5 minutes. See Eli 150c/250c User Guide  |
| Laboratory Assessments                          | X               | X                      |                         | X                       |                 | X                |                  | X                |                  | X                |                  | X                                | Section 9.3.4
Placement of an intravenous lock is allowed for onsite visits when multiple blood draws are required.  |
| Urinalysis                                      | X               |                        |                         | X                       |                 | X                |                  | X                |                  | X                |                  | X                                |   |
| Blood PK Sampling                               | X               | X                      | X                       | X                       |                 | X                |                  | X                |                  | X                |                  | X                                | See section 9.4 for the sample collection schedule. Must be collected prior to administration of study drug.  |

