4.7 SAFETY ANALYSES

Adverse events, including abnormal laboratory findings, will be defined using the National Cancer Institute (NCI) Common Terminology for Adverse Events (CTCAE, version 5), and will be coded according to the most recent Medical Dictionary for Regulatory Activities (MedDRA) version. Adverse events will be summarized according to the MedDRA coded Preferred Terms (PT) by System Organ Class (SOC). Previous and concomitant medications will be coded using the WHO Drug Dictionary version.

The evaluation of safety is based on clinical AEs, vital signs, echocardiogram, ECG results, and clinical laboratory results reported during the study. Cardiac MRI measures

may also be included in the safety assessment. Safety analyses will be performed using the treated subjects. For AEs, all enrolled subjects will be listed.

Safety analysis data displays will be generated for the following:

- the double-blind treatment period, with baseline defined as the last visit prior to the start of the double-blind treatment period
- all active treatment during both the double-blind and open-label treatment periods (excluding data from the placebo subjects during the double-blind period); for this analysis, baseline will be defined as the last visit prior to the start of active treatment for each subject (i.e., the start of double-blind treatment period for those subjects randomized to active treatment from study start, or the start of the open-label treatment period for those subjects randomized to double-blind placebo and who are switching to active treatment at the start of the OLE).

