4.7.3 Laboratory Data

Scheduled laboratory measurements and corresponding change from baseline values will be summarized by treatment and nominal visit for each laboratory test, in SI units.

The results of all protocol-specified clinical laboratory tests, as well as the normal range of laboratory results, will be listed in SI units.

The incidence of marked laboratory abnormalities (based on Roche Standard Reference and Marked Reference Ranges) will be summarized using descriptive statistics, for all parameters for which the Marked Reference Ranges are defined.

For all parameters for which NCI CTCAE grades are defined, summary tables showing the number of subjects with abnormal laboratory results (falling outside of the laboratory range of normal) based on the grading criteria will be provided.

Plots of mean lab test results over time over-plotted on a scatterplot of all subject results at each visit will be provided for alanine aminotransferase (ALT), aspartate aminotransferase (AST), total bilirubin, glutamate dehydrogenase assay, gamma-glutamyl transferase, and creatine kinase (CK).

Scatter plots of post-baseline maximum values will be provided for ALT vs. Total bilirubin and AST vs. Total bilirubin separately.

Double Y-axis trace plots over time will be provided for ALT and CK in the same graph.

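### Boys switched from placebo have no scheduled safety laboratory test for 11 weeks after their first active dose, so transient early abnormalities are under-counted in the SAP's pooled all-active display

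*Protocol*

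**What the plan says.** **First exposure.** For boys who were on placebo in the double-blind phase, active drug begins in the OL phase: "Participants originally randomized to placebo will be randomized to the high or low dose of RO7239361 on Day 1 of the OL phase" (Protocol, Table 2-3). The week numbering starts at the first dose: "The first 3 doses of RO7239361 (Week 1, Week 2 and Week 3) must be administered at the clinic".

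**Safety laboratory schedule.** In Table 2-2 the row "Laboratory Assessments" is marked at Day 1, Day 8, Day 29 and Weeks 12, 24, 36 and 48. In Table 2-3 the row "Laboratory Tests" is marked at OL Week 1 and then at Week 12, with nothing at the Week 2, 3 or 6 visits. It continues at Weeks 24, 36, 48 and later. PK, myostatin and immunogenicity samples are scheduled at OL Weeks 1, 2 and 3.

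**Cardiac schedule.** After first dose, echocardiograms start at Week 12 in Table 2-2 and at OL Week 24 in Table 2-3. ECGs start at Week 24 and at OL Week 48 respectively.

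**Pause criteria.** Protocol Sections 8 and 9.2.7 give four within-subject triggers for pausing dosing. Three rest on ALT (read against CPK) or total bilirubin; the fourth rests on symptoms or signs.

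**Analysis.** SAP 4.7 plans two sets of safety displays. One covers the double-blind period alone. The other covers "all active treatment during both the double-blind and open-label treatment periods (excluding data from the placebo subjects during the double-blind period", with baseline reset to the last visit before active treatment. SAP 4.7.3 summarises scheduled values by nominal visit and adds: "The incidence of marked laboratory abnormalities (based on Roche Standard Reference and Marked Reference Ranges) will be summarized using descriptive statistics". SAP 4.7.6 plans an incidence table for low LVEF. None of these sections says how unequal testing between the two groups is to be handled.

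**The concern.** The all-active display combines two groups whose first weeks on drug are observed differently. A boy started on active who has a brief laboratory abnormality in his first month has two scheduled chances to show it. A boy switched from placebo has none. If such an abnormality clears before OL Week 12 and prompts no unscheduled test, the switched boy enters the denominator without being able to enter the numerator. The pooled incidence is then pulled down, and a reader of the table cannot tell by how much.

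There is also a conduct question. The laboratory-based pause triggers have no scheduled post-dose data in switched boys during those 11 weeks, and the protocol gives no reason for testing less often after first exposure in one phase than in the other.

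**Working it through.** **1. Group sizes.** The plan's 53 per arm is used only to size the groups, and it reproduces closely. With a difference of 2.5, SD 4.4, two-sided 0.05 and 80% power, n = 2 × (1.960 + 0.842)² × 4.4² / 2.5² = 48.6, so 49 per arm. Allowing for 5% discontinuation, 49 / 0.95 = 51.6, so 52 against the stated 53. Fifty evaluable per arm gives power 0.811 against the stated 80%.

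**2. Weeks converted to days since first active dose.** OL Week *n* is (*n* − 1) × 7 days after the first dose, because the first dose is at OL Week 1. As a check, home dosing starts at OL Week 4, which is day (4 − 1) × 7 + 1 = 22 of that phase and matches Day 22 in the double-blind phase. Double-blind Week *n* is *n* × 7 days after first dose, since Table 2-2 labels Day 8 as Week 1 and Day 29 as Week 4.

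| Scheduled after first active dose | Started on active (Table 2-2) | Switched from placebo (Table 2-3) |
|---|---|---|
| First laboratory test | 7 days | 77 days (74–80 with the ±3-day window) |
| Second laboratory test | 28 days | OL Week 24: 161 days |
| Laboratory tests before the Week 12 test | 2 | 0 |
| Laboratory tests up to and including Week 48 | 6 (Day 8, Day 29, Weeks 12, 24, 36, 48) | 4 (OL Weeks 12, 24, 36, 48) |
| First echocardiogram | Week 12: 84 days | OL Week 24: 161 days |
| First ECG | Week 24: 168 days | OL Week 48: 329 days |

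The OL Week 1 laboratory test falls on the first-dose visit. The table does not state its order relative to the dose, and it can serve at most as a baseline.

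**3. Share of switched boys in the pooled display.** 53 × 0.95 ≈ 50 switched, and 2 × 53 = 106 started on active. The share is 50 / (106 + 50) = 50/156 = 32%. If only 40 switch it is 40/146 = 27%; if all 53 switch it is 53/159 = 33%.

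**4. Size of the under-count.** Assume equal true risk in both groups, full detection at Days 8 and 29 in boys started on active, and no unscheduled tests. Let *f* be the fraction of abnormalities that appear and clear before OL Week 12. Then

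relative under-count = *f* × switched / (106 + switched).

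- *f* = 1: 50/156 = 32% (33% if all 53 switch). A true incidence of 5% means 0.05 × 156 = 7.8 boys, of whom 0.05 × 106 = 5.3 are seen. The display shows 5.3/156 = 3.4%.
- *f* = 0.50: 0.50 × 50/156 = 16%.
- *f* = 0.25: 0.25 × 50/156 = 8%.

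The documents give no value for *f*; 0.25 to 0.50 is illustrative.

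**5. Whether limiting the pooled table to Weeks 12, 24, 36 and 48 would help.** It would not. Those weeks exclude Days 8 and 29, so detection of an abnormality that clears before Week 12 falls from 106/156 = 68% to zero. Nor are the visits aligned: OL Week 12 is 77 days after first dose (74–80) and double-blind Week 12 is 84 days (81–87), so the windows do not overlap.

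**The case against.** The strongest reply is that early laboratory risk is already estimated elsewhere. The double-blind display has about 106 boys on active, tested at Days 8 and 29 beside concurrent placebo, and the OL schedule does not touch it. This stands. A reader might infer that early abnormalities are under-counted across the whole trial; the documents support that only for the pooled display.

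Second, the one-third figure is a ceiling. Persistent abnormalities are seen at OL Week 12. Neither group is tested between Week 4 and its Week 12 test, so abnormalities confined to that gap are missed in both. The only liver signal described is a rat transaminase rise that the protocol calls time-dependent (Section 3.3), which is not evidence of an early transient effect in boys. The number switching is also assumed, since entry to the OL phase is optional. All of this stands and limits the size.

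Third, the SAP does not say outright that any post-baseline abnormality counts regardless of testing frequency. That is the natural reading of an incidence table, and the by-visit summaries would simply show no early data for switched boys. This is fair, and it is why the SAP should state the rule.

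Fourth, a reader might infer that the laboratory values cannot be obtained in those weeks, or that the pause criteria do not operate. They are unscheduled, not excluded. Adverse events are monitored at every OL visit, the symptom-based trigger and investigator judgement still apply, and Section 9.3.3 asks for repeat ECG and echocardiogram when new cardiac symptoms appear. However, subjects remain blinded to their original assignment and sites receive assignments only with the final report, so extra testing cannot be aimed at switched boys. A rise without symptoms would prompt no test.

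Fifth, a reader might infer that Tables 2-2 and 2-3 contradict each other. They govern different phases, and nothing says they must match. The clinic doses and observation at OL Weeks 1–3 are explained by hypersensitivity risk (Section 7.7.2.1) and apply to all boys. They do not show that the early laboratory tests were meant to be repeated. What remains is an unexplained difference that bears on the laboratory-based pause triggers.

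**Conclusion.** The point holds for the all-active display only. Abnormalities that appear and clear before OL Week 12 can be recorded at scheduled tests in boys started on active but not in boys switched from placebo, and the SAP pools the two without comment. The bias in that display is downward. Its size is at most about 32–33% in relative terms, and about 8–16% if a quarter to a half of abnormalities are that transient. These figures rest on 40 to 53 switched boys (about 50 at 5% discontinuation; 40 would lower the ceiling to 27%), equal true risk, full detection at Days 8 and 29, and no unscheduled tests. Symptom-prompted tests would reduce them.

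The randomised double-blind comparison and persistent abnormalities are not affected. This is a cheap improvement to a secondary, uncontrolled display, together with a question to the sponsor about the schedule. It does not threaten the trial's main safety conclusions.

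**What to change.** **SAP 4.7, 4.7.3 and 4.7.6.** Present the all-active laboratory and echocardiogram incidence separately for boys started on active and boys switched from placebo, by time since first active dose. State in the text and in table footnotes that switched boys have no scheduled laboratory data between the first-dose visit and OL Week 12. Do not limit the pooled incidence to the nominal weeks that both schedules share. The cost is one extra table split, with no new data.

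**Protocol.** The sponsor should reconcile the safety schedules in Tables 2-2 and 2-3, for boys first exposed at OL Week 1, with the laboratory-based pause criteria in Sections 8 and 9.2.7, or justify the difference. No particular test schedule is proposed here. A justification costs a sentence or two; a change of schedule would need an amendment.
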